5.3 Sample Size Calculation

The sample size calculation was based on the primary objective – determining the effect of *Prehab* on rates of prolonged hospital length of stay > 7 days. Our preliminary data, demonstrated the proportion of frail patients in the Control group with a hospital length of stay > 7 days to be 58.3%. For the *Prehab* group, based on improvements in functional capacity in our pilot *RCT* and the work by Arthur et al14, we believe an absolute 20% reduction in proportion of patients that require prolonged hospital length of stay of greater than 7 days, is feasible. A sample size of 194 individuals (97 in each group) will be required for a two-tailed test at an alpha of 0.05 and power of 80%. All patients assigned to the pilot *Prehab* group completed the intervention, however, we are mindful that we will be recruiting frail, elderly patients who may have a higher dropout rate. Hence, we are estimating a 20% dropout rate and plan to recruit 244 individuals (122 in each study arm) to achieve an eventual sample size of 194 after dropout.

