	
study Data Safety Monitoring Board (DSMB).
 
Safety Monitoring: Clinical stability during the pre-habilitation period is to be evaluated twice per week by the CR team using clinical questioning in comparison to their baseline stress test. All cases will be reviewed in conjunction with the attending physician.

Statistical methods and sample size calculation:	
The sample size calculation was based on the primary objective – determining the effect of Prehab on rates of prolonged hospital length of stay > 7 days. Our preliminary data, demonstrated the proportion of frail patients in the Control group with a hospital length of stay > 7 days to be 58.3%. For the Prehab group, based on improvements in functional capacity in our pilot RCT and the work by Arthur et al.¹⁴, we believe an absolute 20% reduction in proportion of patients that require prolonged hospital length of stay of greater than 7 days, is feasible. A sample size of 194 individuals (97 in each group) will be required for a two-tailed test at an alpha of 0.05 and power of 80%. All patients assigned to the pilot Prehab group completed the intervention, however, we are mindful that we will be recruiting frail, elderly patients who may have a higher dropout rate. Hence, we are estimating a 20% dropout rate and plan to recruit 244 individuals (122 in each study arm) to achieve an eventual sample size of 194 after dropout.

Time schedule:	
Planned start of study: April 2014
 
Planned end of study: May 2017
 
Planned duration: 3.5 years

Table of Contents

Study Synopsis	1
Table of Contents	4
Terms and Abbreviations	8
Executive Summary.....	10
1 General Information	11
1.1 Title.....	11
1.2 Study Management Committee.....	11
1.3 Coordinating Centre	11
2 Background and Rationale for Project	11
2.1 Introduction	11
2.2 Exercise Rehabilitation.....	11
2.3 Identification of Potential Opportunity	12
2.4 The PREHAB Study – Primary Research Questions/Hypotheses	12
3 Study Design.....	12
3.1 Methodological Approach	12
3.1.1 Preliminary Data Informing Study Methodology.....	12

“The PREHAB Study” (Pre-operative Rehabilitation for reduction of Hospitalization After coronary Bypass and valvular surgery.)

3.2 Study Design, Setting, Population.....	14
3.3 Eligibility Criteria	14
3.3.1 Inclusion Criteria (all need to be fulfilled for eligibility).....	14

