3.1.1.1 Frailty in the Cardiac Surgery Population at St. Boniface Hospital

We undertook a systematic review of frailty in the elderly undergoing cardiac surgery (see *Table 2 & Table 3*).(23)(24)(25)(26)(27)(28)(29)(30)(31) This review demonstrated an association with increased frailty and a major negative outcomes ranging from increased institutional care to major adverse cardiac and cerebral event (*MACCE*) and increased in-hospital and long-term mortality after cardiac surgery. However, the lack of a standardized and comprehensive definition of frailty in these studies prevents clarity in understanding the interaction of frailty in the elderly and cardiac surgery. We subsequently completed a prospective examination of frailty in 133 consecutively consenting elderly cardiac surgery patients with high-levels of co-morbid disease (See *Table 4*, *Table 5*, *Table 6* and *Figure 2*). Two definitions of frailty were used (see *Appendix I*): (1) *Modified Fried criteria*: (32)(33)(34) a patient was deemed “frail” if they met ≥ 3 of the following 7 criteria: slowness (5m gait speed)(35), weakness (handgrip strength measurement)(36) and questionnaires assessing self-reported weight loss, exhaustion (the two-item Center for Epidemiologic Studies Depression (*CES-D Scale*), depression (the 5-point geriatric depression scale (*5-GDS*))(37)(38)), low physical activity (the Paffenbarger Physical Activity Index(39)(40)(41)(42)), and cognitive impairment (the Montreal Cognitive Assessment (*MoCA*))(43)(44)(45)). (2) *Short Physical Performance Battery (SPPB)*: a patient was deemed “frail” if his/her composite score was ≤ 9 based on 5m gait speed, balance tests, and the repeated chair stand test (each scored from 0 to 4)(46). Using the modified Fried or the SPPB criteria, 72 (54.1%) or 69 (51.9%) (respectively), patients studied were deemed frail (See *Table 3*). Frail patients were older, more commonly female, had higher *EuroSCORE II* values (a cardiac surgery specific mortality risk prediction score) and lower self-health ratings. Diabetes, cerebrovascular disease (*CVD*), chronic obstructive pulmonary disease (*COPD*), arthritis, anemia, peripheral vascular disease (*PVD*), and lower serum albumin were also significantly associated with being frail. Notably, frailty correlated with clinically important measures of increased hospital *LOS*: total adjusted hospital *LOS* (median 6 days (IQR: 5 – 9) in non-frail vs. 8 days (IQR 6 – 12) in “frail” patients, $p < 0.001$) and a greater proportion of patients in hospital > 7 days (37.7% in non-frail vs. 58.3% in frail patients, $p < 0.02$; See *Table 4 & Table 5*). This longer hospital stay amongst frail patients has implications for increased healthcare costs and we have observed an association between new and persistent mood disorders and reduced engagement in postoperative physical activity with a hospital *LOS* > 7 days after cardiac surgery.

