	After Cardiac Surgery, Frailty is associated with Prolonged Institutional Care	OR 6.3, 95% CI 4.2-9.4
	After Cardiac Surgery, Frailty is associated with Mid-Term Mortality	HR 1.5, 95% CI 1.1-2.2
Singh, 2011	Frailty is associated with Death following Percutaneous Revascularization	HR 5.36, 95% CI 2.41-11.9
	Frailty is associated with MI/Death following Percutaneous Revascularization	HR 3.04, 95% CI 1.80-5.15
Sundermann, 2011	Frailty is associated with one-year mortality after cardiac surgery	OR 1.097, 95% CI 1.038-1.160
Afilalo, 2012	Frailty as measured through gait speed is associated with Mortality or Major Morbidity after CABG and/or valve surgery	OR 2.63, 95% CI 1.17-5.90
Green, 2012	Frailty is associated with increased one year mortality post TAVR	HR 3.16, 95% CI 1.33-7.51
Stortecky, 2012	Frailty is associated with increased all cause mortality one year post TAVI	OR 3.68, 95% CI 1.21-11.19
	Frailty is associated with increased MACCE one year post TAVI	OR 4.89, 95% CI 1.64-14.60
Schoenenberger, 2013	Post TAVI, Frailty is associated with functional decline	OR 3.31, 95% CI 1.21-9.03
	Post TAVI, Frailty is associated functional decline or death	OR 4.46, 95%CI 1.85-10.75

ADL, Activities of Daily Living; MI, Myocardial Infarction; CAF, Comprehensive Assessment of Frailty; MACCE, Major Adverse Cardiac and Cerebrovascular Events; CABG, Coronary Artery Bypass Graft; CHS, Cardiovascular Health Study; MSSA, MacArthur Study of Successful Aging; TAVR, Trans-catheter Aortic Valve Repair; TAVI, Trans-catheter Aortic Valve Implantation; BMI, Body Mass Index; MMSE, Mini Mental State Exam; MNA, Mini Nutritional Assessment; TUG, Timed Get Up and Go test; BADL, Basic Activities of Daily Living; IADL, Instrumental Activities of Daily Living

* study sample size

Table 4 - Characteristics of “not frail” versus “frail” patients, according to the Modified Fried definition of frailty

Pre-Operative Characteristics	Not Frail (N=61)	Frail (N=72)	P-Value
Age (years)	68.7 (7.4)	73.0 (8.2)	0.0023
Female sex	11 (18.0%)	24 (33.3%)	0.0459
BMI (kg/m²)	29.0 (6.0)	29.3 (5.8)	0.8079
Diabetes	13 (21.3%)	29 (40.3%)	0.0190
HbA1c (%)	5.9 (5.7 – 6.6)	6.1 (5.9 – 7.1)	0.2312
CVD	4 (6.6%)	15 (20.8%)	0.0191
COPD	1 (1.6%)	15 (20.8%)	0.0008
Clinical depression	5 (8.2%)	10 (13.9%)	0.3011
Arthritis	5 (8.2%)	17 (23.6%)	0.0171
Angina	37 (61.7%)	50 (69.4%)	0.3479
Smoking history	39 (63.9%)	44 (62.0%)	0.8160
Current smoker	1 (1.6%)	5 (7.0%)	0.2162
Anemia	9 (14.8%)	22 (30.6%)	0.0317

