Albumin (g/L)	39.0 (3.1)	36.4 (4.5)	0.0011
Chronic renal failure	0 (0.0%)	4 (5.6%)	0.1245
Creatinine (μmol/L)	90 (76 – 100)	85 (71 – 116)	0.8231
GI disease	14 (23.0%)	27 (37.5%)	0.0702
PVD	4 (6.6%)	13 (18.1%)	0.0478
Dyslipidemia	40 (65.6%)	51 (70.8%)	0.5155
Pulmonary hypertension	2 (3.3%)	4 (5.6%)	0.6870
Hypertension	48 (78.7%)	65 (90.3%)	0.0624
CHF	30 (49.2%)	40 (55.6%)	0.4631
MI	20 (32.8%)	31 (43.1%)	0.2249
Atrial fibrillation	7 (11.5%)	15 (20.8%)	0.1478
Prior angioplasty or stent	5 (8.2%)	18 (25.0%)	0.0107
Prior cardiac surgery	4 (6.6%)	2 (2.8%)	0.4124
Visual impairment	17 (27.9%)	19 (26.4%)	0.8482
Hearing impairment	3 (4.9%)	5 (6.9%)	0.7260
EuroSCORE II (%)	1.42 (0.87 – 1.94)	2.02 (1.25 – 4.28)	0.0001
Self-health rating (0-4)	3 (2 – 3)	2 (1 – 2)	<0.0001
MoCA score (0-30)	26 (24 – 27)	22 (20 – 25)	<0.0001

“The PREHAB Study” (Pre-operative Rehabilitation for reduction of Hospitalization After coronary Bypass and valvular surgery.)

Table 5 - Intraoperative Variables

Intra-Operative Characteristics	Not Frail (n=61)	Frail (n=72)	P-Value	OR (95% CI)
Procedure type			0.5729	
- Isolated CABG	26 (42.6%)	39 (54.2%)		
- Isolated Valve	19 (31.2%)	17 (23.6%)		
- CABG + Valve	12 (16.7%)	13 (18.1%)		
- Other	4 (6.6%)	3 (4.2%)		
CPB time (minutes)	102 (80 – 132)	89 (68 – 121)	0.1712	

Table 6 - Unadjusted Association of Frailty and Risk of Negative Postoperative Outcome

Post-Operative Outcomes	Not Frail (n=61)	Frail (n=72)	P-Value	OR (95% CI)
ICU LOS (days)	2 (1 – 3)	2 (1 – 3)	0.2819	
Hospital LOS (days)	6 (5 – 9)	8 (6 – 12)	0.0098	
ICU LOS > 72 hours	10 (16.4%)	17 (23.6%)	0.3025	1.58 (0.66 – 3.76)
Hospital LOS > 7 days	23 (37.7%)	42 (58.3%)	0.0177	2.31 (1.15 – 4.65)
Major adverse event	1 (1.6%)	4 (5.6%)	0.3742	3.52 (0.38 – 32.45)
Post-operative Delirium	4 (6.6%)	20 (27.8%)	0.0015	5.48 (1.76 – 17.09)
In-hospital mortality	0 (0.0%)	2 (2.8%)	0.4997	undefined
Discharge to Institution	1 (1.6%)	4 (5.6%)	0.3713	3.64 (0.40 – 33.45)

Categorical variables are listed as frequency values (%), continuous variables are listed as mean (standard deviation) or median (interquartile range). Statistical comparisons were calculated using Chi-Square or Fisher Exact Test for categorical variables, T-Test or Mann-Whitney Test for continuous variables.

Table 7 - Comparison of baseline data between Standard care and Prehab groups

	Standard care (n= 7)	Prehab (n= 7)	P-value
Demographics			
Age (years)	63 ± 3	64 ± 4	0.63
Gender (% female per group)	1 (14%)	2 (25%)	0.99

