Currently, there is little evidence demonstrating the feasibility of a Prehab program for elective CABG patients, with the strongest data showing that exercise therapy and education classes reduce the length of hospital stay by one day and intensive care unit length of stay by 2 hours.⁸ It is also unknown if Prehab programs improve physical fitness prior to elective CABG surgery. Therefore, the purpose of this pilot, randomized controlled trial, was to determine the feasibility of a cardiac Prehab program for patients waiting for elective CABG surgery. We hypothesized that a Prehab intervention would improve physical fitness to a greater extent than current standard care before surgery (preoperatively).

Methods

This pilot study used a randomized controlled trial, parallel two-group ($n = 17$), repeated measures design. We recruited and enrolled patients scheduled to undergo first-time elective CABG surgery from February 2011 to May 2012 (Figure 1) at baseline, preoperatively and three months postoperatively. We included patients with a minimum estimated four week wait-time, with no history of unstable angina, myocardial infarction in the last week, or dementia, ejection fraction >30%, and who were sedentary prior to enrollment. We excluded patients with physical limitations or exercise-induced arrhythmias. Study procedures were initiated following ethical approval from the

[figure not shown]

Figure 1. Flow diagram: participant recruitment.
CABG, coronary artery bypass graft; Preop, one week pre-operatively; Postop, three months post-operatively.

university, regional, and hospital research review committees.

This study was conducted at a 500-bed tertiary center in Western Canada. A research assistant at the tertiary center collected data from all study

participants at baseline, preoperatively, and three months postoperatively. After baseline data collection, the research assistant randomly assigned patients to receive standard care ($n = 9$) or the Prehab intervention ($n = 8$) by opening a sealed envelope

containing a third party, computer-generated random group assignment. The research assistant was aware of which patients were randomly assigned to standard care and Prehab, thus increasing the risk of detection bias.

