We have demonstrated the feasibility of utilizing preoperative exercise therapy for patients waiting for first time elective CABG. Notably, no patients enrolled in Prehab experienced an adverse event, suggesting that a Prehab program may be a safe therapy for patients waiting for a first time elective CABG. Our novel data also shows for the first time that patients who are on a waiting list for elective CABG surgery improve their physical fitness as assessed by the 6MWT before surgery, and that this outcome is maintained postoperatively, as compared with a group that received standard care. Similarly, Prehab improved 5-meter gait speed preoperatively and was maintained postoperatively; whereas, participants in the standard care group had no change in 5-meter gait speed over time. Interestingly, while only three (43%) of the standard care participants chose to enroll in cardiac rehabilitation postoperatively, all eight (100%) participants in the Prehab group had chosen to attend. Collectively, our data suggests that there is an opportunity to utilize a Prehab program to significantly improve the health status of patients waiting for elective CABG. However, the results of our study should be interpreted with caution, and a larger study is needed to establish the safety and efficacy of Prehab.

Physical fitness is an important prognostic factor for predicting adverse cardiac events and mortality. Patients with stable coronary artery disease who walk <419 meters on a 6MWT have a two-fold increased risk of experiencing an adverse cardiac event, as compared with patients who walk >481 meters.²¹ In our patient cohort, all patients walked <419 meters at baseline, which did not change in the standard care group. However, after the Prehab intervention, patients were able to walk >481 meters. Therefore, our innovative study data makes an important contribution to this body of literature, because it is the first to demonstrate that a Prehab program enhances physical fitness among a cohort of patients waiting for elective CABG surgery.

Our data did not show a difference in length of hospital stay between standard care and Prehab

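### Is the sample size at fault because the 20-point effect it targets is not shown by the sources cited for it?

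*Combined protocol and SAP*

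**What the plan says.** Section 5.3, repeated in the synopsis, takes from preliminary data "the proportion of frail patients in the Control group with a hospital length of stay > 7 days to be 58.3" per cent. For the Prehab arm it states "we believe an absolute 20% reduction in proportion of patients that require prolonged hospital length of stay of greater than 7 days, is feasible", resting this on functional-capacity gains in the pilot and on an earlier randomised trial of preoperative rehabilitation. With a two-sided 5% test and 80% power it needs 97 per arm. For losses, "we are estimating a 20% dropout rate and plan to recruit 244 individuals (122 in each study arm"), which is meant to leave 194.

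The source of 58.3% is section 3.1.1.1, which reports "a greater proportion of patients in hospital > 7 days (37.7% in non-frail vs. 58.3% in frail patients". Table 6, titled "Unadjusted Association of Frailty and Risk of Negative Postoperative Outcome", gives the counts: 42/72 frail and 23/61 non-frail. Table 4 shows that the groups were formed "according to the Modified Fried definition of frailty".

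The appended pilot paper says of the earlier trial that "exercise therapy and education classes reduce the length of hospital stay by one day". Of its own result it says "Our data did not show a difference in length of hospital stay between standard care and Prehab" participants.

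**The concern.** Four features of the calculation look weak when set beside the plan's own data.

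- **The baseline rate.** Section 5.3 speaks of a control group, but 58.3% comes from an observational cohort of patients frail by the modified Fried criteria. The trial enrols on a Clinical Frailty Score of at least 3 and below 7, and Fried frailty is assessed but not required.
- **The effect.** Subtracting 20 points gives 38.3%, close to the 37.7% seen in non-frail patients. Read that way, Prehab would have to remove almost the entire excess. That excess is unadjusted, and the frail patients were older and had more comorbidity.
- **The cited trials.** One shows no difference in stay. The other shows one day, in patients whom section 3.1 calls younger and lower-risk.
- **Dropout.** The 20% is introduced by talking about completing the intervention, but is then taken off the analysed sample, although the analysis is by intention to treat and stay comes from hospital records.

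If the true effect were much smaller, a null result might be read as coming from a trial with 80% power when the power for that effect was far lower.

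**Working it through.** **1. The plan's own figure.** Inputs from section 5.3: p1 = 0.583, p2 = 0.383, two-sided alpha 0.05, power 80%. The pooled two-proportion formula, with p̄ = 0.483, is

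n = [1.960·√(2p̄(1−p̄)) + 0.8416·√(p1(1−p1) + p2(1−p2))]² / (p1−p2)²
= [1.960·0.7067 + 0.8416·0.6924]² / 0.04
= (1.3851 + 0.5827)² / 0.04 = 96.8, so 97 per arm.

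Allowing for dropout, 97/0.8 = 121.25, so 122 per arm and 244 in all. Both figures reproduce.

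**2. Power for the stated effect.** Φ[(0.20·√n − 1.3851)/0.6924] gives 80.1% at n = 97 and 88.3% at n = 122.

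**3. Smaller effects, control rate 58.3%.**

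| Difference | Power, 97/arm | Power, 122/arm | n/arm for 80% |
|---|---|---|---|
| 20 points | 80% | 88% | 97 |
| 15 points | 55% | 65% | 174 |
| 10 points | 29% | 35% | 390 |

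With all 122 per arm analysed, about 17.8 points is detectable with 80% power.

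**4. The frail/non-frail gap.** 42/72 − 23/61 = 0.583 − 0.377 = 0.206, and 0.20/0.206 = 0.97. The standard error is √(0.583·0.417/72 + 0.377·0.623/61) = 0.085, so the 95% interval is 20.6 ± 16.7, about 4 to 37 points. The gap compares different patients and is imprecise. It is a benchmark, not a ceiling on what treatment can do.

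**5. The pilot.** Stay was 5.3 ± 1.0 days (n = 7) v 5.1 ± 1.4 days (n = 8). The pooled SD is √[(6·1.0² + 7·1.4²)/13] = 1.23, the standard error is 1.23·√(1/7 + 1/8) = 0.64, and the 95% interval is 0.2 ± 2.16·0.64, about −1.2 to 1.6 days. On a normal approximation only about 4% and 9% of such stays exceed 7 days, so no 20-point fall could have appeared. The pilot does not bear on the target either way.

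**6. One day expressed in points.** Assume every stay shortens by exactly one whole day. In the frail cohort 30 of 72 stayed 7 days or less and the median was 8, so ranks 31 to 37 all left on day 8. At least 7/72 = 9.7 points would therefore be gained. The upper quartile of 12 allows at most 53 patients at 11 days or less, so up to 53 − 30 = 23 could have left on day 8, or 31.9 points. Power at 122 per arm is 33% for 7/72, 58% for 10/72, 74% for 12/72 and 91% for 15/72. A log-normal fit to 8 (6–12) gives about 9.6 points, at the bottom of this range. The documents do not say whether the earlier trial's one day is a mean or a median, or how it was spread over patients.

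**7. Population mix.** Suppose, for illustration, that 70% of those enrolled are Fried-frail; the documents give no such share. The control rate becomes 0.7·0.583 + 0.3·0.377 = 0.521. A 20-point fall from 52% still has about 81% power at 97 per arm. If Prehab instead lowers the rate by the same proportion in everyone (0.521·0.383/0.583 = 0.342), power at 122 per arm is again about 81%. If it removes only the frailty excess, the difference is 0.521 − 0.377 = 14.4 points and power is 62%.

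**8. Dropout.** If 20% of stays are missing for reasons unrelated to prognosis, power is the planned 80%. If all 122 per arm are analysed, it lies between 71% (one fifth of the Prehab arm gains nothing, so the effect is 16 points) and 88%. It is 80% if non-completers keep about 46% of the effect.

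**The case for a change.** The strongest case for acting is this. The section claims 80% power for an effect that no cited study has shown. It does not mention the pilot's null result on stay, and it prints no power for anything smaller. Power falls to 35% at 10 points, and a few sentences would put the reader right without adding a patient.

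Part of that stands. The 58.3% is mislabelled, and 20 points is an ambition, not an estimate. The remainder is weaker than it looks:

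- Section 5.3 calls the effect a belief and cites the pilot for functional capacity, not for stay. The pilot's result on stay is in Table 8 and in the appended paper.
- A power of about one in three for a one-day benefit takes the lowest value that the cohort data allow under a uniform shift.
- The fall in average stay from seven to five days, noted in the pilot paper, does not undermine 58.3%. The frail cohort was recruited from July 2012 to July 2013, after the pilot (February 2011 to May 2012), and still had a median of 8 days.
- The 14.4-point figure needs an assumed case mix and removal of the entire frailty excess, which is the very thing said to be out of reach. It is no better supported than 20 points.

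**Conclusion.** The concern is right about the evidence, but it does not call for a change. Section 5.3 delivers the power it states for the effect it states: 80.1% at 97 per arm and 88.3% if all 122 are analysed. The cited sources neither show nor refute 20 points.

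Resizing would need another effect to aim at, and the documents supply none. Ten points would take 390 analysed patients per arm, against 97. Choosing a demanding target at a size that five centres can recruit is a fair trade-off.

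The source of 58.3% can be traced through section 3.1.1.1 and Table 6, so the reference to a control group is a slip of wording. The meaning of dropout is missing detail: the section takes it off the analysed sample, and anyone with a recorded stay would be kept under intention to treat. Correcting either would alter no result.

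What remains is a matter of interpretation. At 122 per arm the 95% interval for the risk difference has a half-width of about 12 points (1.96·0.6924/√122 = 0.123). A non-significant result could therefore leave a useful benefit open, and an analyst would see that from the interval. These figures assume a control rate of 58.3%, equal arms and the unadjusted pooled test.
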